12.3.6 Overall and progression-free survival

Overall survival is defined as the time of study enrolled to death from any cause; patients who remain alive will be censored at the time of last follow-up. Progression-free survival is defined as time from study enrollment to death or disease progression.

12.3.7 Percentage of patients who remain on immunosuppression

We will score patients as remaining on immunosuppression at 1 year if they remain on immunosuppressants at 1 year after the date of their stem cell infusion.

13.0 CRITERIA FOR REMOVAL FROM STUDY

Patients will be removed from study if any of the following events occurs:

- If at any time the patient is found to be ineligible for the protocol as designated in the section on *Criteria Subject Eligibility*, the patient will be removed from the study.
- If subject withdraws consent for continued participation. Management will depend on where they are in their treatment course. Such patients will receive appropriate supportive care.
- Grade II-IV acute GVHD or chronic GVHD develops. If a patient is in the middle of a cycle, the patient may finish their cycle and then will be removed from study.
- Malignant disease relapse, progression, or death occurs.
- If a patient experiences severe unexpected adverse events, the treating physician or primary investigator can remove the patient from study at their discretion.

14.0 BIOSTATISTICS

This is a single arm phase 2 trial to investigate the efficacy of a weekly ixazomib regimen to reduce recurrent or late onset acute and chronic GVHD. The primary endpoint of this study is the incidence of recurrent or late acute grade II-IV aGVHD or chronic GVHD from the time of enrollment (day +100 to +150) to 1-year post-transplant time point. In addition to GVHD, the additional treatment failure criteria listed in 12.2 are considered as failures for the primary endpoint. Patients are evaluable for the primary endpoint if they complete at least one cycle of therapy. Patients who discontinue therapy prior to completing one cycle therapy for reasons unrelated to toxicity will be replaced. Patients who prematurely discontinue therapy after completing at least one cycle of therapy will remain evaluable for the primary endpoint.

The historical benchmark for this study is based on patients enrolled on MSK protocol 06-150. With these data, the estimated grade II-IV acute or chronic GVHD at 1-yr post-transplant among patients who could have been eligible to enroll on this study is 63% (no

patient died for reasons unrelated to GVHD). Therefore, the trial is designed such that a one-year incidence of recurrent or late acute grade II-IV GVHD or cGVHD of 40% would be considered promising for further development, whereas a 60% incidence would not be considered worthy of further study. Using these thresholds, we will utilize a Simon's two-stage optimal design based on the proportion of patients who develop GVHD. If more than 10 of the initial 18 patients have recurrent or late acute grade II to IV or cGVHD, the trial will terminate early due to lack of efficacy. Otherwise, the trial will continue to the maximum sample size of 46. If at the end of the study at least 23 out of 46 patients are free of recurrent or late acute grade II-IV GVHD or cGVHD the intervention will be considered promising for further development. The type I and type II errors are both set at 0.10.

In order to reduce patient risk, the study design includes early termination in the event of excessive graft failure or treatment-related mortality during the study period. Stopping rules for excessive failure and corresponding power calculations are given below. The calculations are based on marginal probabilities.

Failure type	Number of failures needed to suspend the study	Failure rate in the population	Probability boundary is crossed
Secondary graft failure	2 in the first 20	0.02	0.1
	3 at any point	0.15	0.98
Transplant-related 1 yr. mortality	4 in the first 10	0.10	0.07
	5 in the first 20		
	7 in the first 30		
	8 in the first 40	0.30	0.96
	9 at any point		

In addition to the primary objective, there are a number of secondary and safety endpoints included in this study:

Secondary endpoints:

1. Cumulative incidence of cGVHD following study enrollment will be estimated. This will be calculated overall and by severity (moderate/severe). Disease progression and death in the absence of cGVHD are considered competing risks for this analysis.
2. The cumulative incidence of TRM from the time of study enrollment will be estimated, treating disease progression as a competing risk.
3. The cumulative incidence of disease progression from the time of study enrollment will be estimated, treating death in the absence of disease progression as a competing event.
4. The cumulative incidence of grade II-IV and III-IV acute GVHD will be estimated. Disease progression and death in the absence of acute GVHD are considered competing risks for this analysis.
5. Kaplan-Meier methods will estimate overall and progression-free survival from the time of study enrollment.
6. The proportion of patients who are able to discontinue all immunosuppressive medication at one year will be estimated along with a 95% confidence interval.
7. Graphical and summary measures will be used to describe CD3+CD4+ and CD3+CD8+ populations during the study window.

Exploratory Endpoint:

1. The proportion of patients who are able to get vaccines on time will be reported with an exact 95% confidence interval. The vaccine response will be similarly described. Both timing and response will be estimated separately for each vaccine.
2. The treatment failure endpoint will be described separately for patients who enroll on study day +100 to day +125 and for patients who enroll on study day +125 to day +150.

Safety Endpoint:

1. The frequency and severity of adverse events will be tabulated.

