The results of a prospective phase II trial assessing peri-transplant rituximab with a NMA conditioning regimen for patients with CD20 B cell NHL was recently published by Sauter et al from the adult transplantation group at Memorial Sloan Kettering Cancer Center¹⁶. The data from this study ($n = 51$) reveals a promising 2-year event-free survival (EFS) in this group of patients; the EFS was 84% and 40% for chemosensitive as compared to chemotherapy refractory patients before allo-HSCT. The cumulative incidence of grade II-IV aGVHD at 3 and 6 months after HSCT was 18% (95%CI: 7-29) and 25% (95%CI: 13-38), respectively, whereas the cumulative incidence of severe grade III-IV aGVHD at 3 and 6 months was 8% (95%CI: 0-16) and 11% (95%CI: 3-24), respectively. The cumulative

incidence of moderate to severe cGVHD at 1 year was 14% (95%CI: 3-24) and at 2 years was 29% (95%CI: 15-44). Notable, GVHD was noted to be a more frequent cause of death than disease relapse or progression. The number of patients who suffered a transplant-related event (most of which were due to GVHD) was 20 (19%), while the number of patients who relapsed or progressed was 14 (13%). In particular, in those patients with FL, there was one disease-related event and 9 transplant-related events. In a follow-up analysis as of September 1, 2014, 46 patients were alive without progression of disease at day 100. Of those, the development of any GVHD syndrome was assessed. This analysis demonstrated a cumulative incidence of 63% (95%CI: 47-76) at 1-year of any GVHD syndrome. Thirty-five percent (n = 16) had no active GVHD whereas 30 patients had active GVHD syndrome. The predominant manifestation was late onset aGVHD (n = 9, 19.5%) and overlap syndrome (n = 9, 19.5%), followed by classical chronic GVHD (3 interrupted, 4 de novo) and recurrent aGVHD (n = 5, 11%) (unpublished data).

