9.2 GVHD prophylaxis

Ixazomib beginning between day +100 to +150 at a dose of 4 mg orally once per week (3 weeks on/ 1 week off). The patients will continue on this same dose until taper off from immunosuppressants or 1 year post-HSCT is reached (whichever occurs first) or until the patient develops GVHD or malignant disease relapse/progression occurs. Patients who reach 1 year post-HSCT or discontinue immunosuppressants mid-cycle should complete their current cycle of ixazomib.

- The levels of the drug will not be monitored while the patients are on study.
- In order for patients to receive drug, they must have a platelet count > 75K, Hgb (untransfused) > 8 and an ANC > 1.0 (can be supported with G-CSF)
- If more than 2 doses in a row or more than 3 doses total are held, the patient is removed from study.
- Doses are given weekly +/- 3 days

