12.1 CRITERIA FOR THERAPEUTIC RESPONSE/OUTCOME ASSESSMENT

12.2 Criteria for therapeutic response for the primary endpoint

The primary aim is to assess the efficacy of ixazomib for the prevention of recurrent or late grade II-IV aGVHD or chronic GVHD by 1-year post-transplant. Therapeutic response will be determined by the absence of grade II-IV aGVHD or chronic GVHD diagnostic features (or any of the other failure criteria listed in 12.2) during the study window

Patients who receive at least one cycle of therapy will be considered evaluable for the primary endpoint.

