12.3 Criteria for treatment failure for the primary endpoint

- Study drug is discontinued and unable to resume due to drug related toxicity.
- New onset or recurrence of grade II-IV aGVHD (including GVHD flares).
- New onset of chronic GVHD.
- Administration of systemic therapy for treatment of GVHD.
- Development of secondary graft failure during the administration of the study drug.
- Mortality (transplant or treatment-related)

If treatment failure criteria is met, the patient will be removed from the study. A 30-day follow-up will be conducted for end-of-treatment evaluation for toxicity assessment. This follow-up may be conducted via phone call or in-person by the clinical team.

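### The replacement rule lets a patient who stops ixazomib in cycle 1 because of GVHD, the primary outcome, be swapped for a new patient instead of counted as a failure

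*Combined protocol and SAP*

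**What the plan says.** Section 14.0 runs the primary endpoint "from the time of enrollment (day +100 to +150) to 1-year post-transplant time point" and treats the additional failure criteria as failures too. (It cites 12.2 for that list; the list now stands under 12.3.) A patient is evaluable only on completing at least one cycle, and "Patients who discontinue therapy prior to completing one cycle therapy for reasons unrelated to toxicity will be replaced".

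Other sections bear on the same patients:

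- Section 12.2 states evaluability differently: "Patients who receive at least one cycle of therapy will be considered evaluable for the primary endpoint".
- Section 12.3 lists "New onset or recurrence of grade II-IV aGVHD (including GVHD flares") and new chronic GVHD as failures, with no time limit. Stopping for drug-related toxicity is a separate item on that list.
- Section 9.2 (GVHD prophylaxis) continues ixazomib until immunosuppression ends or 1 year is reached, "or until the patient develops GVHD or malignant disease relapse/progression occurs". Section 1.0 says much the same.
- Section 13.0 removes patients who develop grade II-IV acute or chronic GVHD, but adds: "If a patient is in the middle of a cycle, the patient may finish their cycle and then will be removed from study".
- Section 3.1 describes the benchmark cohort: "46 patients were alive without progression of disease at day 100", with a 63% one-year incidence of any GVHD syndrome. It states no condition about completing a treatment period.

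**The concern.** GVHD in the first 28 days is a primary-endpoint failure under Section 12.3. Under Section 14.0, stopping drug for it before the cycle ends is a stop unrelated to toxicity, because 12.3 separates toxicity from GVHD. The patient is then not evaluable and a new patient takes the place. The same gap covers graft failure or transplant-related death in cycle 1 that is not attributed to toxicity.

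The option in Section 13.0 to finish the cycle does not close the gap. It is permissive, it sits awkwardly with Section 9.2, and it makes the counting of an event depend on what the treating team decides after seeing it.

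The boundaries for 18 and 46 patients assume that every enrolled patient's GVHD outcome enters the count. Removing early failures raises the GVHD-free proportion, weakens the stage-1 futility stop and raises type I error. It also compares a set that survived one cycle with a benchmark that had no such condition. With no control arm, nothing in the data would reveal the bias.

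**Working it through.** **Inputs from the documents.** Section 14.0: unpromising incidence 60% (GVHD-free 0.40); promising 40% (GVHD-free 0.60); stop if more than 10 of 18 have GVHD (at most 7 GVHD-free); promising if at least 23 of 46 are GVHD-free; both errors set at 0.10. Section 9.1.1: 28-day cycle. Enrollment on day 100 to 150 leaves 365 − 150 = 215 to 365 − 100 = 265 days to one year.

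**Assumption.** q, the share of enrolled patients replaced because of cycle-1 GVHD, is not in the documents, so a range is shown.

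**1. Reproduce the design.** With GVHD-free probability p,

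P(promising) = Σ (x = 8 to 18) Bin(x; 18, p) × P[Bin(28, p) ≥ 23 − x].

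- p = 0.40: type I error 0.0952; P(stage-1 stop) 0.563.
- p = 0.60: power 0.9004.

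A search for the Simon optimal design returns the same boundaries. The slack is 0.10 − 0.0952 = 0.0048.

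**2. Effect of replacement at a true 60% incidence.** Among counted patients the failure rate is (0.60 − q)/(1 − q), so p = 0.40/(1 − q). Average replacements per 46 evaluable patients are 46q/(1 − q).

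| q | Replaced per 46 | Failure rate among counted | Type I error | P(stage-1 stop) |
|---|---|---|---|---|
| 0 | 0 | 0.600 | 0.095 | 0.563 |
| 0.5% | 0.23 | 0.598 | 0.100 | 0.556 |
| 1/47 = 2.1% | 1 | 0.591 | 0.117 | 0.533 |
| 2/48 = 4.2% | 2 | 0.583 | 0.142 | 0.503 |
| 4/50 = 8.0% | 4 | 0.565 | 0.201 | 0.443 |

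Solving for q: type I error is 0.10 at q = 0.50%, 0.15 at 4.8% and 0.20 at 7.9%.

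**3. How large q might be.** These onset patterns are assumptions, each scaled to 60% by the end of the window of T days. The share with onset by day d is 0.60 × d/T if uniform, 1 − 0.40^(d/T) if the hazard is constant, and 1 − 0.40^((d/T)^k) for a Weibull with shape k. For example, with T = 240 and d = 28, the uniform pattern gives 0.60 × 28/240 = 0.070 and type I error 0.184. Constant hazard gives 0.101 and 0.242.

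Type I error for T from 265 down to 215 days, all such cases replaced:

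| Onset pattern | Onset by day 28 | Onset by day 15 (third dose) |
|---|---|---|
| Weibull, shape 2 | 0.105–0.111 | about 0.099 |
| Weibull, shape 1.5 | 0.128–0.142 | 0.107–0.112 |
| Uniform | 0.173–0.198 | 0.132–0.142 |
| Constant hazard | 0.224–0.266 | 0.154–0.171 |

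If only half are replaced, constant hazard gives 0.148–0.162 (day 28) or about 0.12–0.13 (day 15).

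The documents do not settle the pattern. In Section 3.1, median acute GVHD onset was day 123 in the series given sirolimus, tacrolimus and methotrexate, mostly during tapering. Section 9.1 recommends tapering from about day 100 for sibling donors. Both point to early events. The recommended taper from about day 180 for unrelated donors points to later ones.

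**The case against.** The text gap itself is hard to dispute; the objections are to its size and weight.

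- **Other failures offset it.** Section 14.0 also counts toxicity stops, graft failure and mortality. If these add 2 percentage points of failure to a 60% GVHD rate, type I error is 0.056 with no replacement, 0.070 at q = 2% and 0.095 at q = 5%. With 1 point it is 0.091 at q = 2% and 0.122 at q = 5%. This is correct arithmetic, but it moves the true failure rate above the 60% at which the plan defines its error. It does not reverse the bias.
- **The benchmark is 63%.** At that rate the false-positive probability is 0.042 with no replacement, 0.053 at q = 2%, 0.073 at q = 5%, and 0.10 at about q = 8%. This is useful context, but the plan sets its null at 60% ("whereas a 60% incidence would not be considered worthy of further study").
- **The large figures are worst cases.** With dosing three weeks on and one off, there may be no cycle-1 dose left to stop after about day 15, and patients may finish the cycle. This is fair: the day-15 column may be the more realistic one.
- **Early onset is weakly supported.** The day-123 median includes events before day 100 (range 17–268), whereas enrollees have no active GVHD. In the rituximab trial in Section 3.1, grade II-IV acute GVHD rose from 18% at 3 months to 25% at 6 months, about 2 points per 28 days. That omits recurrent acute and chronic GVHD, so it is only a partial guide. Even q = 2% gives 0.116.
- **Intent is clear enough.** Section 12.3 lists GVHD without a time limit, so staff would probably count it. That is a reasonable reading, but the explicit replacement sentence says otherwise, and a go/no-go rule should not rest on unwritten practice.

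**Conclusion.** The rule is wrong as written. Read literally, it replaces patients who have reached the primary outcome, contrary to Section 12.3 and to an endpoint that starts at enrollment. The direction is certain: a replaced patient is a sure failure exchanged for one who may succeed.

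The size is not known. It ranges from nothing, if every affected patient finishes the cycle, to roughly double the nominal error at four replacements per 46. Because the slack is under 0.005, q = 0.5% is enough to reach 0.10. These figures assume a true 60% failure rate and independent patients; additional non-GVHD failures or a higher true rate would lower them.

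Two lesser inconsistencies belong with this point. Section 12.2 requires patients to *receive* one cycle, while 14.0 requires them to *complete* it. Cycle-1 toxicity stops are failures in 12.3 and are not replaced under 14.0, yet they fail its evaluability condition.

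The point must be fixed, because it decides who enters both the futility look and the final decision.

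**What to change.** In Sections 12.2 and 14.0:

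- State that a patient with any failure event on the Section 12.3 list after the first dose is evaluable, counts as a failure and is not replaced, whether or not the cycle was finished.
- Limit replacement to patients who leave before completing cycle 1 without a listed failure event. Say explicitly how an event between enrollment and first dose is handled; counting it agrees with an endpoint that starts at enrollment.
- Apply the 18- and 46-patient boundaries to this set, and say whether they count GVHD alone or every listed failure.
- Use one evaluability term throughout, correct the cross-reference to the failure list, and reconcile Sections 9.2, 12.2, 12.3, 13.0 and 14.0. Which rule governs stopping drug at GVHD is a clinical matter; the counting rule should not depend on it.
- Report the number of replacements and the reason for each.

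The cost is a wording amendment. Sample size and boundaries stay as they are, with exact type I error 0.095 at a 60% failure rate and power 0.900 at 40%. The observed failure rate may be slightly higher because early failures now count.

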9.1 TREATMENT/INTERVENTION PLAN

Patients will be cared and monitor according to the allogeneic BMT clinical care guidelines.
https://one.mskcc.org/sites/pub/corp/bmt/Documents/H3_Allo%20Guidelines_01_27_2016.pdf

Patients will have received a calcineurin inhibitor based GVHD prophylaxis with either tacrolimus or cyclosporin in combination with methotrexate. The study drug will be initiated between day 100 to 150 post-allograft.

Tapering of calcineurin inhibitor (CNI) will follow the institutional practice. For recipients of HLA-matched sibling donor, is recommended to initiate CNI taper around day 100 and taper at 10-25% decrements every 2 weeks. For recipients of HLA-matched unrelated and HLA-mismatched unrelated donors, is recommended to initiate CNI taper around day 180 and taper at 10-15% decrements in 4 weeks intervals.

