
 All hematologic toxicities 	
 For hematologic toxicity that occurs during a cycle but recover in time for the start of the next cycle,: 
 If dose was reduced within the cycle, start the next cycle at that same dose. If due to toxicity timing, i.e. after Day 15 dosing thus a dose reduction was not required at that point in the cycle, reduce ixazomib by 1 dose level at the start of that cycle. Do not reduce the dose both within a cycle and at the start of the cycle for the same most severe toxicity.

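### The Section 14 replacement rule has no exception for GVHD, so a primary-endpoint failure in cycle 1 could be replaced and not counted

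*Combined protocol and SAP*

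**What the plan says.** Section 14.0 runs the primary endpoint from enrollment (day +100 to +150) to one year after transplant, so cycle 1 lies inside the window. The same paragraph sets two conditions on the denominator: "Patients are evaluable for the primary endpoint if they complete at least one cycle of therapy" and "Patients who discontinue therapy prior to completing one cycle therapy for reasons unrelated to toxicity will be replaced". Section 12.2 states evaluability in slightly different words: "Patients who receive at least one cycle of therapy will be considered evaluable for the primary endpoint".

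Section 12.3 lists the failure criteria, with no minimum exposure. They include "New onset or recurrence of grade II-IV aGVHD (including GVHD flares") and, separately, new chronic GVHD. A patient who meets one is removed from the study.

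GVHD also ends dosing. Under Section 9.2 (GVHD prophylaxis) ixazomib continues "until the patient develops GVHD or malignant disease relapse/progression occurs", and Sections 1.0 and 3.3 say much the same. Section 13.0 adds an option for GVHD that appears during a cycle: "If a patient is in the middle of a cycle, the patient may finish their cycle and then will be removed from study".

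The decision rule in Section 14.0 stops the trial if more than 10 of the first 18 patients have GVHD. It calls the regimen promising if at least 23 of 46 are GVHD-free. Both error rates are set at 0.10.

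**The concern.** The only exception to replacement is toxicity. A patient who develops grade II-IV acute or chronic GVHD after the first or second dose, and stops because the protocol says to stop, has left before completing a cycle for a reason unrelated to toxicity. That meets the replacement rule as written. Section 12.3 suggests such a patient is meant to be a failure, but it does not say who is evaluable. Sections 12.2 and 14.0 do say, and they leave this patient out.

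Whether a primary event is counted can then depend on a dosing choice made after the event, in an open-label single-arm trial. Because this route drops failures and never successes, taken alone it favors ixazomib at both the 18-patient and the 46-patient look.

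**Working it through.** **Inputs from Section 14.0.** Unpromising GVHD incidence 60%, promising 40%, historical benchmark 63%. Continue if at most 10 of 18 have GVHD; promising if at most 23 of 46 have GVHD.

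**Formula.** With g the GVHD incidence among counted patients,

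P(promising) = Σ over x = 0 to 10 of Bin(x; 18, g) × P[Bin(28, g) ≤ 23 − x].

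**The plan's own design.** P(promising) is 0.0952 at g = 0.60 and 0.9004 at g = 0.40. The stage 1 stopping probability at 0.60 is 0.563. A search for the Simon optimal design returns the same boundaries, so the stated design reproduces. At 63%, P(promising) is 0.042.

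**Effect of replacement.** Let p be the true incidence and q the share of enrolled patients who have GVHD in cycle 1 and are replaced. The incidence among counted patients becomes g = (p − q)/(1 − q).

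| p | replaced per 46 enrolled | g | P(promising) | stage 1 stop |
|---|---|---|---|---|
| 0.60 | 0 | 0.600 | 0.095 | 0.563 |
| 0.60 | 1 | (0.60 − 1/46)/(1 − 1/46) = 0.591 | 0.117 | 0.533 |
| 0.60 | 2 | (0.60 − 2/46)/(1 − 2/46) = 0.582 | 0.144 | 0.500 |
| 0.63 | 1 | 0.622 | 0.054 | 0.638 |
| 0.63 | 2 | 0.613 | 0.068 | 0.609 |

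At p = 0.60 the 0.10 limit is reached at q = 0.0050, which is 0.0050 × 46 = 0.23 of a patient.

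**How large q might be (assumptions).** The documents give no cycle-1 GVHD rate. I assume dosing starts at enrollment and a follow-up window of W = 365 − 150 = 215 to 365 − 100 = 265 days. On the three-weeks-on schedule the last cycle-1 dose falls on day 15 (Section 9.1.1 mentions toxicity "after Day 15 dosing thus a dose reduction was not required at that point in the cycle"), so about L = 14 days are at risk of an early stop. Uniform onset gives q = pL/W; constant hazard gives q = 1 − (1 − p)^(L/W).

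- p = 0.60, all stop at onset: q runs from 0.60 × 14/265 = 0.0317 to 1 − 0.40^(14/215) = 0.0579, that is 1.5 to 2.7 of 46. P(promising) is 0.129 to 0.165.
- p = 0.60, half stop at onset: 0.111 to 0.126.
- p = 0.63, all stop at onset: 0.061 to 0.084.
- p = 0.40, all stop at onset: q = 0.021 to 0.033, and P(promising) is 0.925 to 0.937.
- Outer bound, L = 28, W = 215, constant hazard, all stop: q = 0.1125 and P(promising) = 0.266 at p = 0.60. The same model at p = 0.63 gives 0.154.

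**Offset from the other failure criteria.** Section 14.0 says these also count as primary failures, although its decision rule names GVHD only. If 5% of GVHD-free patients fail in other ways (assumption), total failure is 0.60 + 0.40 × 0.05 = 0.62. P(promising) is then 0.056 without replacement and 0.079 to 0.103 with q = 0.0317 to 0.0579.

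**The case against.** The strongest reply is that the literal reading is not the intended one. The endpoint runs from enrollment, Section 12.3 requires no minimum exposure, and a replacement rule is most naturally aimed at dropouts with no outcome. Replacing under-exposed patients is familiar in phase 2, and toxicity dropouts are expressly kept. This is a fair guess at intent, but no sentence states it, and it leaves two readings of the primary denominator.

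Section 13.0 also lets patients finish the cycle, which would make them evaluable. That narrows the gap without closing it, because the option is permissive and the dosing sections end treatment at GVHD.

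The secondary cumulative-incidence analyses in Section 14.0 state no one-cycle requirement, so the event could still appear there. That is right, but those analyses do not drive the go/no-go rule.

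The objections to size carry more weight. Cycle-1 timing and stopping behavior are assumed. At the 63% benchmark it takes about 3.7 replaced patients per 46 to reach 0.10. With the 5% offset it takes about 2.5. Early events may also be rarer than assumed: Section 3.3 links GVHD to the immunosuppression taper, and for unrelated-donor recipients Section 9.1 says it "is recommended to initiate CNI taper around day 180", which is after enrollment. These points limit the likely effect but do not repair the rule.

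**Conclusion.** The concern holds. Followed as written, the rule can drop primary-endpoint failures, and the bias from this route runs in one direction. At the plan's own 60% threshold, a single replaced GVHD patient per 46 enrolled is enough to exceed the stated 0.10. The 14-day scenarios put the error at about 0.11 to 0.165, depending on whether half or all of these patients stop at onset.

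The text is clear; confidence in the size is only moderate, because it rests on assumed onset timing and on how many patients stop at onset. It is nil if all finish the cycle, and it may be largely cancelled if other failure types enter the decision rule. This should be corrected, though the documents do not show that the trial's conclusion would change.

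**What to change.** In Sections 12.2 and 14.0, state that any patient who has taken at least one dose of ixazomib and meets a Section 12.3 failure criterion is evaluable, counts as a failure and is not replaced, whether or not cycle 1 was completed. Limit replacement to patients who leave during cycle 1 before meeting any failure criterion. The finish-the-cycle option in Section 13.0 can stay, because counting would no longer depend on it.

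The cost is one clarifying sentence in each of the two sections. Treatment, sample size, stopping boundaries and data collection do not change. With every cycle-1 GVHD event counted, the GVHD decision rule keeps its designed type I error of 0.095 and power of 0.900.

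### The primary endpoint is declared as a composite, but the 60%/40% rates and both Simon decision rules are worded in GVHD alone, so the event to be counted is not fixed.

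*Combined protocol and SAP*

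**What the plan says.** **Endpoint.** Section 14.0 first gives the primary endpoint as the incidence of recurrent or late grade II-IV acute GVHD, or chronic GVHD, from enrollment to 1 year after transplant. It then widens it: "the additional treatment failure criteria listed in 12.2 are considered as failures for the primary endpoint". Section 12.2 defines response the same way, as "the absence of grade II-IV aGVHD or chronic GVHD diagnostic features (or any of the other failure criteria listed in 12.2" and so on. The list itself stands under 12.3, although both places cite 12.2. Besides GVHD and systemic GVHD therapy it contains "Study drug is discontinued and unable to resume due to drug related toxicity", secondary graft failure on study drug, and "Mortality (transplant or treatment-related" death).

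**Decision rule.** Section 14.0 sets 40% GVHD as promising and 60% GVHD as not worth pursuing, from a historical GVHD figure of 63%. It adopts a Simon "two-stage optimal design based on the proportion of patients who develop GVHD". The trial stops at stage 1 "If more than 10 of the initial 18 patients have recurrent or late acute grade II to IV or cGVHD". It is promising at the end if "at least 23 out of 46 patients are free of recurrent or late acute grade II-IV GVHD or cGVHD". Both error rates are set at 0.10. No sentence says that the two counts include the non-GVHD failures.

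**The concern.** The endpoint and the rule that decides the trial describe different events. Take an evaluable patient who permanently stops ixazomib for drug toxicity and has no GVHD. Section 12.3 makes that patient a failure for the primary endpoint. The stage 1 and final rules, as worded, do not count that patient as a failure.

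This affects the futility stop and the only go/no-go decision. If the counted event is left open, it could be settled after results are known. The stated error rates also cannot be attached to the declared endpoint until the plan says whether 60%/40% are GVHD rates or composite failure rates.

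**Working it through.** **1. Inputs from Section 14.0.** Stage 1 has n = 18 and stops if more than 10 have the event. The total is N = 46, and the result is promising if at least 23 are free of the event, that is, at most 23 have it. The null event rate is 0.60 and the target is 0.40. Both error limits are 0.10.

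**2. Reproducing the design.** With p the probability of the counted event,

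P(promising | p) = Σ (x = 0 to 10) Bin(x; 18, p) × P(Bin(28, p) ≤ 23 − x).

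- p = 0.60 gives 0.0952 (type I error).
- p = 0.40 gives 0.9004 (power).

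A full search for Simon's optimal design with these inputs returns the same sample sizes and boundaries. The arithmetic is sound, and these figures hold for whichever event has the 0.60 and 0.40 rates.

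**3. Boundary cases.**

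| Data | Rule as worded (GVHD) | Declared endpoint (composite) |
|---|---|---|
| 23 of 46 with GVHD, 1 other patient with a non-GVHD failure | 23 free: promising | 22 free: not promising |
| 10 of 18 with GVHD, 1 other patient with a non-GVHD failure | 10 events: continue | 11 events: stop |

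**4. Composite counted, 60%/40% kept as GVHD rates.** The documents give no rate of failure without GVHD, so q = 2%, 5% and 10% are assumed, in two forms:
- Absolute: q is the share of all patients who fail without GVHD, so p = g + q, with g the GVHD rate.
- Net: q is the probability of an independent non-GVHD failure, so p = 1 − (1 − g)(1 − q).

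| | q = 2% | q = 5% | q = 10% |
|---|---|---|---|
| p at g = 0.40, absolute | 0.42 | 0.45 | 0.50 |
| Power | 0.850 | 0.745 | 0.508 |
| p at g = 0.40, net | 0.412 | 0.43 | 0.46 |
| Power | 0.872 | 0.819 | 0.703 |
| p at g = 0.60, absolute | 0.62 | 0.65 | 0.70 |
| Type I error | 0.056 | 0.022 | 0.003 |
| p at g = 0.60, net | 0.608 | 0.62 | 0.64 |
| Type I error | 0.078 | 0.056 | 0.031 |

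Power reaches 0.80 at p = 0.4356, which is 3.56 points above 0.40, or 46 × 0.0356 = 1.6 patients.

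**5. How often the two counts disagree.** A composite result that is promising is always promising on GVHD alone, so the probability of opposite verdicts is a difference. At 40% GVHD with absolute q it is 0.9004 − 0.8500 = 0.050, 0.9004 − 0.7454 = 0.155, and 0.9004 − 0.5080 = 0.392.

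**6. Secondary illustration only.** If GVHD alone were counted while 60% was meant as the composite failure rate, then p = 0.60 − q = 0.58, 0.55 and 0.50 (absolute), and P(promising) would be 0.150, 0.263 and 0.508. This mixes a GVHD count with a composite null, a pairing that the plan does not state.

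**The case against.** The best defence is that the composite is plainly meant. The sentence that widens the endpoint comes before any boundary, Section 12.2 repeats it, and the heading of 12.3 ties the list to the primary endpoint. GVHD in the boundaries would then be shorthand. The remark about the historical patients, that no "patient died for reasons unrelated to GVHD", suggests the authors checked that 63% also served for death. Section 12.3 also removes a failing patient from study with a 30-day toxicity follow-up, so such a patient need not have been shown to be GVHD-free at 1 year.

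Much of this stands: the composite is the more natural reading. It does not close the gap. The text of both decision rules, the design basis and the two rates still say GVHD. The historical remark covers death only. It says nothing about graft failure and cannot cover toxicity of a drug those patients did not receive.

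Three stronger readings might be inferred and are not supported.
- **The false-positive risk is inflated.** If the composite is counted against GVHD rates, type I error stays at or below 0.095. If the rates and boundaries are both read as GVHD, the stated errors hold exactly. Inflation needs the mixed reading in step 6.
- **A single patient will usually decide the trial.** This happens only on a boundary. At 40% GVHD, exactly 10 of 18 has probability 0.077, and continuing to finish at exactly 23 of 46 has probability 0.037.
- **Non-GVHD failures will be frequent.** The documents give no rate. The adverse event frequencies for ixazomib are not discontinuation rates, and the held-dose rule in the GVHD prophylaxis section is not limited to drug toxicity.

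**Conclusion.** The inconsistency is real and should be resolved before the eighteenth patient is scored. The declared endpoint is a composite, while the rates and both decision rules are worded as GVHD. The Simon calculation itself is not at fault.

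On the natural composite reading the consequence is lost power, not a higher false-positive risk. The planned 0.90 at 40% GVHD becomes 0.85, 0.75 or 0.51 at 2%, 5% or 10% absolute failure without GVHD, or 0.87, 0.82 or 0.70 if these are net independent probabilities. The direction is certain for any rate above zero. The size rests wholly on assumed rates, and the 10% column should not be read as a forecast.

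**What to change.** Use one event throughout.

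1. Because the protocol declares the composite, word both boundaries in it: stop if more than 10 of the first 18 patients meet any failure criterion in Section 12.3; promising if at least 23 of 46 meet none.
2. Correct the references to 12.2 in Sections 12.2 and 14.0 so that they point to 12.3.
3. State what the error rates refer to. Type I error 0.095 and power 0.900 hold if 60%/40% are composite failure rates. If they remain GVHD rates, replace the 0.90 power with a value at a stated assumption for failure without GVHD.

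If the sponsor prefers GVHD alone as the decision event, the composite sentences in Sections 12.2 and 14.0 must change to match.

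**Cost.** N = 46 and the boundary numbers do not change. Reading 60%/40% as composite rates is more than rewording, because it makes the bar harder in GVHD terms. A 40% composite rate means 40 − 5 = 35% GVHD if 5% fail for other listed reasons, or 40 − 10 = 30% if 10% do. The 63% benchmark cannot settle that choice, since it cannot be adjusted for study-drug toxicity. The sponsor has to make it as a judgement and record it.
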